6.3.1.3. Efficacy – Bacteriological Endpoint (culture)

Same set of analyses, as in the PCR efficacy bacteriological endpoint, will be performed in the subset of subjects for whom the culture sputum (collected at AECOPD visits) is performed

Approximately 50% of the subjects will be allocated to sputum culture analysis (depending on which site the subject belongs as not all sites are qualified and selected for culture analysis).

The selection of sites that will perform the sputum culture is based on site characteristics (i.e., presence of qualified laboratory) and only subjects enrolled in these sites will be considered for this analysis.

CONFIDENTIAL

207489 (NTHI MCAT-002)

Statistical Analysis Plan Amendment 2 FDA Final Draft

The analysis will be performed in the culture-subset of the modified TVC (mTVC) population. The mTVC is defined as all subjects in TVC (ES) and in the subset for culture sample who provide valid culture sputum sample results.

6.3.2. Additional considerations

6.3.2.1. Clinical endpoint

Number of AECOPD

The number of AECOPD occurring during the 1 year follow-up period starting 1 month post-Dose 2 will be used to describe vaccine efficacy (VE). Exacerbation rate reported during this period will be calculated for each subject.

Only for the purpose of reporting summary statistics, the number of exacerbations during the 1-year follow-up will be imputed for subjects withdrawing from the study to provide an estimate of the number of exacerbations over the follow-up period. This calculation will only be performed for the descriptive statistics for the rate of exacerbations during 1 year follow up period since the modelling of exacerbations takes into account the number of exacerbations and the time of follow-up for each subject [see Section 11].

Control of type I error

Inferential analyses for efficacy are planned to be performed at alpha level of 0.13 (two sided). No alpha adjustment for multiple testing in the secondary endpoints will be performed, nevertheless efficacy analysis, both primary and secondary endpoints will be also complemented with the 95% CI.

6.4. Immunogenicity and Cell-mediated Immunity (CMI)

6.4.1. Analysis of immunogenicity planned in the protocol

As first line, the immunogenicity analysis will be based on the PPS (ATP). If the percentage of vaccinated subjects with serological results excluded from the PPS for analysis of immunogenicity is more than 10%, a second line immunogenicity analysis will be performed on the TVC.

Within group assessment

For each group (i.e., vaccine and placebo), at each timepoint during which blood samples are collected for humoral immune response (i.e., Day 1, Day 31, Day 61, Day 91, Day 271 and at Day 451), and for each vaccine strain (i.e., PD, PE, PilA and UspA2), the following will be computed:

- Seropositivity* rate and the associated exact 95% CI
- GMCs and the associated 95% CI

CONFIDENTIAL

207489 (NTHI MCAT-002)

Statistical Analysis Plan Amendment 2 FDA Final Draft

* Seropositivity rate is defined a percentage (proportion) of seropositive subjects.

Seropositive subject is a subject whose antibody concentration is greater than or equal to the assay cut-off value, as specified in [Table 2](#).

Descriptive statistics

The \log_{10} ELISA concentration and fold increase over pre-exposure (i.e., Day 1) will be tabulated via descriptive statistics such as N, mean, SD, median, min, max and 95% CI for each group, study visit (where immune blood draw is performed) and vaccine strain.

Similarly, the proportion of seropositivity subjects will be tabulated together with N, number of seropositive subjects and percentage for each group, study visit and vaccine strain.

In addition, the distribution of antibody concentrations for each strain will be displayed using Reverse Cumulative Distribution Curves (RCDF).

The percentages of subjects with positive (see [Table 2](#)) ELISA values (on \log_{10} scale) will be plotted via RCDF, having the individual concentration on the X-axis and the percentage of subject with equal to or greater than the value on the Y-axis by strain and visit.

Between groups assessment

The between groups immunogenicity analysis will be carried out with an alpha =0.05, however these are descriptive comparisons with the aim to characterize the difference between groups and should be interpreted with caution considering that there will be no alpha adjustment for multiplicity.

GMCs and GMCs ratio

The difference between vaccine and placebo will be evaluated in terms of GMCs ratio (Vaccine/Placebo) and it will be tabulated for each time together with the 95% CIs of the GMC ratio between groups by using an ANCOVA model on the logarithm base10 transformation of the concentrations. This model will include the group (vaccine or control), age category (40 - 59 years or 60 - 80 years), GOLD grade (GOLD 2, GOLD 3 or GOLD 4) and country as fixed effects and pre-Dose 1 concentration (as covariate).

For each vaccine group and time point (Visit), adjusted GMCs, GMC ratios and their 95% CIs will be obtained by exponentiating (base 10) the least square means and the lower and upper limits of the 95% CIs of the \log_{10} -transformed concentrations. These will be obtained from an ANCOVA with vaccine group, age category, GOLD grade, country and pre-Dose 1 concentrations, as implemented in the following SAS code:

```
PROC GLM data=<dataset>;
  BY visit;
  class trt age gold country;
  MODEL log(titer) = trt age gold country log(prettier);
  LSMEAN trt / CL PDIFF ALPHA=0.05;
  RUN;
```

CONFIDENTIAL

207489 (NTHI MCAT-002)

Statistical Analysis Plan Amendment 2 FDA Final Draft

Seropositivity: proportion and difference between proportions.

The vaccine group difference will be also evaluated in terms seropositivity proportion difference calculated using a binomial distribution. For constructing the 2-sided 95% CIs for the difference between groups the usual normal approximation is not considered to be appropriate because these proportions could be close to 1. Therefore, the associated confidence interval for the differences in percentage will be constructed using the MN method [Miettinen and Nurminen, 1985]. In analyzing differences in proportions, the MN method assumes normality of the test statistic (or a chi-square distribution for the squared version) under the null hypothesis and the difference with the usual method is in the variance estimation. This method is implemented in SAS with the following code:

```
PROC FREQ data= <dataset>;
  TABLES trt*count / RISKDIFF(CL=MN) ALPHA=0.05;
  WEIGHT frequency / zero;
  RUN;
```

Table 2 Humoral Immunity (Antibody determination)

System	Component	Method	Kit / Manufacturer	Unit*	Cut-off*	Laboratory
SERUM	anti-PD antibody	ELISA	In house	EU/ml	153	GSK Biologicals ** or GSK designated laboratory
	anti-PE antibody				16	
	anti-PiA antibody				8	
	anti-UspA2 IgG antibody				28	

EU/ml = ELISA unit per millilitre

* Assay cut-off and unit might be subject to change during the course of the study (e.g. in case of assay re-optimization, qualification, (re)validation or standardization). In this case, this will be documented in the clinical study report.

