6.3.1.1. Efficacy – Clinical Endpoints**6.3.1.1.1. Primary Analyses**

The primary analysis method of the vaccine VE will consider the exact inference on the risk ratio (R_{vacc} / R_{con}) based the total number of moderate and severe AECOPD observed in 1 year time of follow up.

VE is defined as: $VE = 1 - R_{vacc} / R_{con}$

being

- R_{vacc} = average yearly incidence rate of AECOPD events per subject in the group 10-10-3-AS.
- R_{con} = average yearly incidence rate of AECOPD events per subject in the placebo group.

Inferential statistic

Incidence rates and VE with 87% and 95% CIs will be tabulated for primary efficacy endpoint. P-value (to test $H_0 = [VE=0]$) will be tabulated for the primary endpoint.

The efficacy of vaccine in preventing moderate and severe AECOPD will be demonstrated if the lower limit of the two-sided 87% CI of VE is above 0.

The primary outcome will be analysed using the Negative Binomial regression model with number of AECOPD as dependent variable; treatment (vaccine or placebo), age group (40 - 59 yrs or 60 - 80 yrs), GOLD grade (2, 3 or 4) and history of moderate and severe exacerbations (<2 or ≥ 2) and country as independent variables, with logarithm as link function, and the logarithm of time for follow-up (in days) as an offset variable.

The following SAS code will be applied for primary analysis:

```
PROC GENMOD data=<dataset>;
  CLASS trt age gold hexac country;
  MODEL nb_exac = trt age gold hexac country
    / dist=NegBin LINK=log OFFSET=logfu alpha=0.13;
RUN;
```

Where

trt= treatment arm;
 age= Age Group;
 nb_exac=number of exacerbations;
 gold= GOLD grade at enrolment;
 hexac= History of moderate/severe exacerbation;
 country=Subject Country;
 fu= follow up time in days;
 logfu= log(fu);

CONFIDENTIAL

207489 (NTHI MCAT-002)

Statistical Analysis Plan Amendment 2 FDA Final Draft

Point estimate and CIs of the incidence rate for each arm, will be computed using a simple Negative Binomial model, without covariates and thus the following SAS code will be applied:

```

PROC GENMOD data=<dataset>;
BY trt;
MODEL nb_exac =           / dist =NegBin LINK=LOG OFFSET=LOGFU alpha=0.05;
ODS OUTPUT ParameterEstimates=out_parm NObs=Nobs;
RUN;

DATA parm_est(keep= val rate rate_LL rate_UL);
SET out_parm(WHERE=(Parameter='Intercept'));
format rate rate_LL rate_UL 8.2;
val= "Yearly Rate from Negative Binomial";
rate=EXP(Estimate)*365;
rate_LL=EXP(LowerWaldCL)*365;
rate_UL=EXP(UpperWaldCL)*365;
RUN;

```

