11.3. Randomization method and minimization algorithm

Subjects are randomised using a centralised randomisation system on internet (SBIR) at first dose. The system incorporates a minimization algorithm based on White SJ and Freedam LS method [[White SJ](#), Freedman LS, 1978] and it is described below:

Notation:

- k input values to be used for minimization, each with a weight w_k ($k=1, \dots, K$) and l_k variants.
- i treatment groups applicable to stratum the subject has been identified with randomization ratio a_1, \dots, a_i
- D: percentage of determinism
- W: weight assigned to each minimization factor

In this study k=4: Country, GOLD grade, History of exacerbation and Age group defined as :

COUNTRY [8 variants]: BE CA FR DE IT ES UK US

GOLD [3 variants]: 2 3 4

AGECAT [2 variants]: 40-60 61-80

HIST_ES [2 variants]: < 2 >=2

i=2: VACCINE and PLACEBO with randomization ratio 1:1 ($a_i=1$)

D=90%

W=1 for each variable

CONFIDENTIAL207489 (NTHI MCAT-002)
Statistical Analysis Plan Amendment 2 FDA Final Draft

Algorithm:

For a new subject in criteria levels $s_1 \dots s_k$ **Step 1: Minimization computation**

Step 1.1: Initialize Problem flag to 0

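### The GMC ANCOVA in SAP 6.4.1 omits exacerbation history, the fourth minimisation factor: no bias as randomised, at most slightly wide intervals, and a one-term fix

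*SAP*

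**What the plan says.** All references are to the current SAP (Amendment 2).

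- **Allocation (section 11.3).** The algorithm uses four factors: "In this study k=4: Country, GOLD grade, History of exacerbation and Age group defined as" the levels listed there. Each has weight 1, determinism is 90%, and the allocation is "VACCINE and PLACEBO with randomization ratio 1:1". History enters as "HIST_ES [2 variants]: < 2 >=2" and age as "AGECAT [2 variants]: 40-60 61-80".
- **GMC model (section 6.4.1).** The between-group analysis of log10 concentrations is an ANCOVA by visit. The text gives its terms as follows: "These will be obtained from an ANCOVA with vaccine group, age category, GOLD grade, country and pre-Dose 1 concentrations". The code agrees: "MODEL log(titer) = trt age gold country log(prettier" (the pre-dose term closes the list). Age is split differently from the allocation: "age category (40 - 59 years or 60 - 80 years".
- **Efficacy models (sections 6.3.1.1.1 and 6.3.1.2).** The primary negative binomial model has "MODEL nb_exac = trt age gold hexac country", where hexac is exacerbation history (<2 or ≥2). The bacteriological efficacy model uses the same covariates.
- **Status of the GMC comparison.** Section 6.4.1 works at alpha 0.05, calls the between-group comparisons descriptive and applies no multiplicity adjustment. The first-line set is the PPS. Section 5.1.6 evaluates its exclusions separately for each strain and time point.

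The SAP gives no reason for leaving history out of the GMC model.

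**The concern.** When allocation forces the arms to be alike on a factor, that factor contributes almost nothing to the variance of the treatment contrast. If it also predicts the outcome and is left out of the model, its variation stays in the residual. The standard error then describes more variability than the design allows. Fitting the balancing factors removes the mismatch, and the SAP's main efficacy models do fit history together with the other three.

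The GMC model keeps country, GOLD grade and a version of age, and drops only history. Humoral immunogenicity is a secondary objective, and the adjusted GMC ratios with their 95% intervals are its modelled between-group result. What is at stake is a little precision in those intervals. There is also some protection of the ratio itself if exclusions from the PPS disturb the balance on history.

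**Working it through.** The SAP states no power, precision or coverage figure for the GMC comparison, so there is nothing of its own to reproduce. The check compares the factor lists and then bounds the effect.

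**1. Factor lists**

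| Factor | Minimisation (11.3) | GMC ANCOVA (6.4.1) | Primary model (6.3.1.1.1) |
|---|---|---|---|
| Country | 8 levels | included | included |
| GOLD grade | 2, 3, 4 | included | included |
| Age | 40-60 / 61-80 | 40-59 / 60-80 | 40-59 / 60-80 |
| Exacerbation history | <2 / ≥2 | **absent** | <2 / ≥2 |

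Two factors match the allocation exactly. Age matches except for subjects aged 60, who change category. History is absent.

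**2. Analytic size**

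Let R² be the share of the residual variance of log concentration that history explains once the planned terms, including the pre-dose value, are fitted. With balanced arms, and ignoring the single degree of freedom:

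- narrowing of the interval when history is added = 1 − √(1 − R²)
- width of the planned interval relative to the fuller model = 1/√(1 − R²)

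| Assumed R² | Narrowing | Relative width of planned interval |
|---|---|---|
| 0 | 0 | 1.000 |
| 0.005 | 1 − √0.995 = 0.25% | 1.003 |
| 0.01 | 1 − √0.99 = 0.50% | 1.005 |
| 0.02 | 1 − √0.98 = 1.0% | 1.010 |

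The R² values are assumptions.

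**3. Simulation of the allocation**

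The check used 3000 trials of 600 subjects (about 300 per arm, as in section 2), with the section 11.3 algorithm and no true group effect. Several inputs were assumed: equal country shares, GOLD grades at 45/40/15%, uniform age, and history split about evenly. All 600 subjects were analysed, with no exclusions.

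- The mean absolute difference between arms in the number of subjects with one level of history was 0.87, so the factor is almost perfectly balanced at allocation.
- With history in the model, 95% coverage was 95.0% at every assumed R².
- For the planned model:

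| Assumed R² | Coverage | Relative width |
|---|---|---|
| 0 | 94.9% | 1.000 |
| 0.01 | 95.1% | 1.005 |
| 0.05 | 95.5% | 1.026 |
| 0.10 | 96.0% | 1.054 |
| 0.20 | 97.0% | 1.118 |

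The widths agree with the formula. The Monte Carlo standard error of a single coverage figure is √(0.95 × 0.05/3000) = 0.4 percentage points, so 95.1% at R² = 0.01 cannot be told from nominal. The rows from 0.05 upward show how the effect grows. Nothing in the SAP suggests that history explains that much.

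**4. Cost in degrees of freedom**

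The planned model has 1 (intercept) + 1 (group) + 1 (age) + 2 (GOLD) + 7 (country) + 1 (pre-dose) = 13 parameters. With 600 subjects the residual degrees of freedom go from 587 to 586.

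**The case against.** The case for leaving the model alone is reasonable.

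- **It is a consistent, prespecified model.** Text and code agree, the same covariates stand in all three SAP versions, and the SAP nowhere promises that every model will adjust for every minimisation factor. This is true. It shows the omission is not a slip in one line of code, but it gives no reason for it.
- **The link between history and titre is conjecture.** History is an obvious covariate for exacerbation counts. Nothing in the SAP says that it predicts antibody level once the pre-dose concentration is in the model. This stands: the range must start at zero.
- **No decision depends on it.** The comparisons are descriptive, and any error is towards wider intervals. This also stands and limits the importance.
- **Other analyses omit factors too.** The Cox models in 6.3.1.1.2 leave out country, and the seropositivity difference is unadjusted. True, but that does not make this omission right.
- **Balance is not assured in the PPS.** Minimisation balances randomised subjects, not visit-specific subsets. This weakens the claim that the intervals must be too wide. It is equally a reason to fit the factor, because adjustment then protects the ratio against whatever imbalance the exclusions produce.

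Three stronger readings are tempting. A reader might infer that the planned intervals are definitely too wide, but that needs an association the SAP does not document. A reader might infer that the GMC ratio is biased; as randomised, it is not. A reader might also infer that adding history would make the model match the allocation exactly. It would not, because the age cut-points differ.

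**Conclusion.** The point holds as a minor one. The GMC ANCOVA leaves out one of the four factors used in the minimisation, without explanation, while the SAP's primary and bacteriological efficacy models include it. The GMC ratio is unbiased as randomised. The planned 95% intervals are too wide by nil to about 1% for a partial R² of 0 to 0.02. That range is assumed, and it presumes that balance on history survives into the analysis set. Coverage at such values is indistinguishable from 95%. The primary efficacy conclusion is untouched. The reasons to act are that the improvement costs almost nothing, brings the model closer to the allocation and the efficacy models, and offers some protection in the PPS.

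**What to change.** In section 6.4.1, add exacerbation history (hexac, <2 or ≥2) to the CLASS statement, to the MODEL statement and to both places in the text that list the ANCOVA covariates. The variable is already used in the efficacy models, so no new data or derivation is needed, and the model loses one degree of freedom. If the protocol fixes the covariate set for this analysis, record the addition in section 9, which at present reports no changes from the planned analyses. If the omission is deliberate, one sentence giving the reason would be enough.

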6.4.2. Analysis of CMI planned in the protocol

CMI analysis will be descriptive only and it will be performed in a subset of approximately 120 subjects for whom the CMI blood samples are collected (*see protocol* section 5.1 Number of subjects).

CMI analysis will be based on the PPS (ATP). If more than 10% will be excluded from the PPS for CMI, a second line CMI analysis will be performed on the CMI subset of the TVC (i.e., All subjects with at least 1 documented study vaccine administration and for whom CMI data are available).

CONFIDENTIAL

207489 (NTHI MCAT-002)

Statistical Analysis Plan Amendment 2 FDA Final Draft

NTHi and Mcat - specific CMI responses as measured by flow cytometry ICS**Descriptive statistics**

For each vaccine strain (PD, PE, PilA and UspA2) the frequency of specific CD4⁺T-cells producing two or more markers (see [Table 3](#)) will be summarised by means of descriptive statistics (mean, SD, minimum, Q1, median, Q3, and maximum) for each group, and at each time point during which blood samples are collected for CMI subset (Day 1, Day 91, Day 271 and Day 451).

The frequency of CD4+ T-cells producing two or more markers upon in vitro stimulation with the antigen (induction condition) is presented per million of CD4+ T cells for the analysis and in percentage for the graphical representation (via BOX-plot).

The Geometric Mean (GM) frequency at each CMI timepoint (Day 1, Day 91, Day 271 and Day 451) and for each stimulation (vaccine antigen) will be also computed by taking the anti-log of the mean of the log frequency transformations.

Table 3 Intracellular cytokines staining (Markers)

Method	Unit	Cytokine	Cytokine Label
Flow cytometry ICS	Number of specific CD4+T-cells /10 ⁶	CD40L	CD40 Ligand
		IL-2	interleukin 2
		IL-13	interleukin 13
		IL-17	interleukin 17
		IFN- γ	interferon gamma
		TNF- α	tumour necrosis factor alpha

T helper profile

T helper profile of the specific CD4+ and CD8+ T cells response will be evaluated with the frequencies of antigen (stimulation) specific CD4⁺/ CD8⁺ T-cells expressing T helper 1, T helper 2 and T helper 17 specific markers (IFN- γ , IL-13 and IL-17 respectively) and will be summarised by means of descriptive statistics (mean, SD, minimum, Q1, median, Q3, and maximum) for each group and at time point: Day 1, Day 91, Day 271 and Day 451 and via BOX plot.

6.4.3. Additional considerations**Humoral immune response**

Missing immunogenicity data are considered missing completed at random (MCAR) and therefore will not contain information that impact the results of the analysis (i.e., not informative). Imputation methods will therefore not be used.

Antibody concentrations below the assay cut-off will be given an arbitrary value of half the assay cut-off for the purpose of geometric mean concentration (GMC) calculation.

CONFIDENTIAL207489 (NTHI MCAT-002)
Statistical Analysis Plan Amendment 2 FDA Final Draft**Cell-mediated immune response**

The frequency of CD4+ T-cells expressing a marker (see [Table 3](#)) is presented per million of cells for the analysis and per hundred cells for the graphical representation.

The frequency of antigen-specific CD4+ T-cells for each individual subject is calculated as the difference between the frequency of CD4+ T-cells producing at least 2 cytokines, upon *in vitro* stimulation with the antigen (induction condition) minus the frequency of CD4+ T-cells producing at least 2 cytokines upon *in vitro* stimulation in medium only (background condition).

$$Freq_{Induction}^{2+} = \frac{n_{Induction}^{2+} - n_{background}^{2+}}{1000000} \quad Log_e(Freq_{Induction}^{2+}) = Log_e(\frac{n_{Induction}^{2+} - n_{background}^{2+}}{1000000})$$

$n_{Induction}^{2+}$ = Number of antigen-specific CD4+T-cells expressing two or more cytokines.

Each data will be obtained by subtracting the summary of the background value to each summary value. Values less than or equal to zero will be set to 1 for the purpose of geometric mean calculation and graphical representation.

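### The CMI formula in SAP Section 6.4.3 contradicts the stated per-million scale, and the replacement value 1 for non-positive results has no unit

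*SAP*

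**What the plan says.** The scale is given three times in the current SAP (Amendment 2):

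- Section 6.4.2 says that the frequency "is presented per million of CD4+ T cells for the analysis and in percentage for the graphical representation (via BOX-plot".
- Table 3 gives the unit as "Number of specific CD4+T-cells" per 10^6.
- Section 6.4.3 repeats that the frequency "is presented per million of cells for the analysis and per hundred cells for the graphical representation".

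Section 6.4.3 then displays a formula. The frequency is the induction count minus the background count, divided by 1,000,000, and the natural log is taken of that quotient. The replacement rule follows: "Values less than or equal to zero will be set to 1 for the purpose of geometric mean calculation and graphical representation". Section 6.4.2 defines the geometric mean as "computed by taking the anti-log of the mean of the log frequency transformations".

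**The concern.** Read as printed, the formula gives a proportion between 0 and 1, while the text and Table 3 call for a count per million. Nothing says which prevails. The 1 that replaces non-positive results has no unit, and the SAP does not say whether it is inserted before or after rescaling. The same number can therefore mean three things: 1 cell per million, all cells (1,000,000 per million), or 1% of cells (10,000 per million). The first is a floor. The second is the ceiling of the scale. The third is very high beside responses of a few hundred per million.

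CMI is a secondary objective, and Section 8 places it in the Priority 1 clinical study report. No test is planned, so the summaries and plots are themselves the result that will be read. The subset has about 60 subjects per group (Section 2), so a few misplaced records can move a geometric mean a long way.

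**Working it through.** The SAP gives no CMI figure to reproduce. The check is what the rule does on each scale.

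**General result.** Let d be the background-subtracted value per million and p the share of records with d ≤ 0. The geometric mean (GM) is exp(mean of log x).

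- Per-million scale: floored records contribute log(1) = 0, the log of 1 per million.
- Formula scale, replacement after division: floored records again contribute log(1) = 0, but a response of 1 per million is now log(10^-6) = -13.8. Converted back to per million, the GM is larger by (10^6)^p = 10^(6p).

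This gives 10^0.6 ≈ 4 at p = 10%, 10^1.2 ≈ 16 at 20% and 10^1.8 ≈ 63 at 30%. No distributional assumption is needed.

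**Three illustrative records: 400, 150 and -20 per million.**

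- Per million: (400 × 150 × 1)^(1/3) = 39 per million.
- Formula, replacement after division: (0.0004 × 0.00015 × 1)^(1/3) = 0.003915, or 3,915 per million. The ratio is 100 = 10^(6/3).
- Percent scale for graphs: the responders plot at 0.04% and 0.015%. A replacement of 1 made on that scale plots the third record at 1%, or 10,000 per million, which is 25 times the highest genuine response (10,000/400).

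**Group comparison.** The inputs below are assumptions, because the SAP gives neither shares of non-positive values nor response levels. Each group has n = 60, with all positive values in a group held at one level.

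| Share ≤ 0, vaccine / placebo | Level per million, vaccine / placebo | GM ratio, per million | GM ratio, formula with replacement after division |
|---|---|---|---|
| 0% / 10% | 500 / 100 | 7.9 | 2.0 |
| 5% / 10% | 500 / 100 | 5.8 | 2.9 |
| 5% / 20% | 500 / 100 | 9.2 | 1.2 |
| 5% / 30% | 500 / 100 | 14.6 | 0.46 |
| 10% / 50% | 1000 / 50 | 70.9 | 0.28 |
| 20% / 20% | 500 / 100 | 3.6 | 3.6 |

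For the 5% / 30% row, the per-million GMs are 500^0.95 = 366.5 and 100^0.70 = 25.1. On the formula scale they become 366.5 × 10^0.3 = 731 and 25.1 × 10^1.8 = 1,585 per million.

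The order changes when (1 - p_placebo) × log(level_placebo × 10^-6) exceeds (1 - p_vaccine) × log(level_vaccine × 10^-6). With 5% floored in the vaccine group and levels of 500 and 100, that needs more than about 22% floored in placebo. Over vaccine shares of 0% to 10% and level pairs 300/100, 500/100 and 1000/50, the break-even runs from about 12% to 37%.

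**The case against.** The strongest defence is that the analysis scale is stated three times as per million, and on that scale 1 is a low floor. The printed divisor may be no more than unit notation, as in Table 3. The replacement can also be read as applying to the subtracted difference, since the sentence just before the rule describes that subtraction. A difference set to 1 and then divided gives 10^-6, again a low floor. All of this is fair, and a per-million floor is very probably what was meant.

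It is also true that CMI is descriptive only (Sections 6.4.2 and 7), with no test or ratio planned. The rule is confined to geometric means and graphs, so the tabulated mean, median, quartiles and extremes are untouched. An absurd geometric mean beside a sound median might well be noticed.

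This does not clear the text. The formula still contradicts the stated scale. The rule expressly covers graphs, which are in percent, so the per-million reading does not settle what is plotted.

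A reader might infer that the rule as such gives non-responders the largest value and reverses vaccine and placebo. The documents do not support that. The first part needs the proportion scale, against three contrary statements, and replacement after division. The second also needs clearly more non-positive values in placebo, which the SAP does not report.

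**Conclusion.** Section 6.4.3 is internally inconsistent, and the unit and timing of its replacement value are undefined. The harm is conditional. On the per-million reading there is none. With the printed formula and replacement after division, the geometric mean is inflated by exactly 10^(6p). With replacement on the percent scale, non-responders plot at 10,000 per million. A change in the order of the groups is possible only under assumed shares of non-positive values: it appears in some of the scenarios above and not in others.

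The affected outputs are the descriptive CMI geometric means and graphs. The primary endpoint and all planned tests are untouched. The wording should still be corrected, because it is an error in a stated rule for a secondary endpoint and is easily put right.

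**What to change.** In Section 6.4.3:

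1. Define the frequency as the induction value minus the background value for cells with two or more markers, both per million CD4+ T cells, and remove the further division by 1,000,000 from both the frequency and its log.
2. State that values at or below zero are set to 1 per million before the log is taken.
3. State that conversion to percent for graphs comes after this step, so that the floor plots at 0.0001%.

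The cost is a few words in the SAP and one line of programming. No data collection or other analysis changes.
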